### **Modified Hidradenitis Suppurativa Score**

Summary statistics will be provided for absolute and percent change from baseline of modified Sartorius score by visit up to Week 52 for each treatment group.

### **HS-Physician's Global Assessment**

The number and percentage of subjects who achieve HS-PGA response will be presented by visit up to Week 52 for each treatment group, where HS-PGA response is defined as the achievement of at least a 2-point reduction in HS-PGA score compared to baseline or the achievement of a “mild” status (defined as achieving an HS-PGA score of  $\leq 2$ ).

### **CRP and ESR**

Summary statistics will be provided for absolute and percent change from baseline of CRP and ESR by visit up to Week 52 for each treatment group.

## **2.14 Week 52 and Week 16 databases**

Any changes to the Week 16 PEA HiSCR responder status as a result of changes to baseline or Week 16 lesion counts will be listed and assessed for the impact on the PEA. Additionally, any changes to the AN50 responder status, NRS30 responder status, flare and percentage change from baseline in AN count will be listed.

Changes to the treatment termination reason will also be listed in a separate listing.

Further, any new SAEs with start date prior to the cut-off date of the Week 16 PEA iDBL will be listed. All SAEs related to the Week 16 analysis that have been recorded or modified after the cut-off date and the SAEs with changed preferred term with start date prior to the cut-off date will be included.

## **3 Sample size calculation**

Sample size requirements for this study are primarily driven by HiSCR at Week 16 endpoint. A 5% two-sided type-I-error rate will be used to control for type-I-error. Two secukinumab doses will be tested versus placebo with respect to the primary endpoint (HiSCR at Week 16). The type-I-error will be split to 4% and 1% two-sided for secukinumab 300 mg Q2W vs. placebo and secukinumab 300 mg Q4W vs. placebo, respectively. Sample sizes will be based on this type-I-error assumption.

A total of 471 subjects was originally planned to be randomized to study drug in a 1:1:0.5:0.5 ratio. A second study of identical design with the same sample size will be conducted in parallel. Both studies are independently powered to address the primary endpoint (HiSCR) and secondary endpoints of AN count and flare. The secondary endpoint of pain will be analyzed in the combined populations of both trials, provided the primary null-hypothesis can be rejected in both studies. All sample size calculations were done in nQuery Advisor 7.0.

As discussed in Section 5 of the study protocol, to account for the disruptive impact of the COVID-19 pandemic on the conduct of the study since the release of protocol Amendment 01, the number of randomized subjects was increased to approximately 541 (15% increase from the original population of 471 subjects).

### **Primary endpoint**

HiSCR: Based on adalimumab phase III placebo-controlled studies (PIONEER I and II, respectively, [Kimball et al 2016](#)), a placebo response rate of 30% is assumed. The total sample size of 471 subjects for this trial is sufficient to achieve 93% power for the demonstration of 20% difference of secukinumab 300 mg Q2W over placebo based on the primary endpoint (HiSCR) when assuming a secukinumab response rate to be 50%. In regards to the comparison of secukinumab 300 mg Q4W to placebo, we achieve 83% power to show superiority. The sample size was further increased by 15% to 544 subjects to account for potential pandemic impact.

### **Secondary endpoints**

The power mentioned for the Secondary endpoints is conditional on the successful rejection of the null hypothesis for the primary endpoint (HiSCR), and the testing procedures are defined in Section 2.8 in the week 16 PEA SAP.

Percentage change in AN count: based on adalimumab phase III placebo-controlled studies (PIONEER I and II, respectively, [Kimball et al 2016](#)), it is assumed that the difference between secukinumab and placebo is at least 18% in favor of secukinumab when considering the mean percentage change from baseline in AN count at Week 16. Although it is planned to use an ANCOVA model for the analysis, an approximate sample size can be based on a simple *t*-test. A total sample size of 471 subjects is sufficient to achieve 92% power in secukinumab 300 mg Q2W vs. placebo and 81% power in secukinumab 300 mg Q4W vs. placebo when assuming a standard deviation of 46%.

Flare: Based on adalimumab phase III placebo-controlled studies (PIONEER I and II, respectively, [Kimball et al 2016](#)), a placebo rate of 35% is assumed. A total sample size of 471 subjects is sufficient to achieve 98% power for the demonstration of 20% difference of secukinumab 300 mg Q2W over placebo based on the second endpoint when assuming secukinumab 300 mg Q2W rate to be 15%. Assuming the same rate for secukinumab 300 mg Q4W, the sample size would be sufficient to achieve 92% power in a comparison of secukinumab 300 mg Q4W vs. placebo.

Pain: Based on adalimumab phase III placebo-controlled studies (PIONEER I and II, respectively, [Kimball et al 2016](#)), a placebo rate of 23% is assumed. Assuming 80% subjects are qualified to calculate Pain variable NRS30, a total sample size of 942 subjects across two studies is sufficient to achieve 85% power for the demonstration of 13% difference of secukinumab 300 mg Q2W over placebo based on the second endpoint when assuming the rate to be 36%. The sample size is also sufficient to achieve 70% power to demonstrate superiority of secukinumab 300 mg Q4W over placebo based on the same assumptions in regards to the rates of secukinumab and placebo as above.

## 4 Change to protocol specified analyses

Response of HS-PGA is defined as the achievement of at least a 2-point reduction in HS-PGA score compared to baseline or the achievement of a “mild” status (defined as achieving an HS-PGA score of  $\leq 2$ ). While in the Protocol it is defined as at least a 2-point reduction in HS-PGA score only.

## 5 Appendix

### 5.1 Imputation rules

#### 5.1.1 Study drug

Any partial dates will be imputed as follows:

The earlier day will be taken from below

- The last day in the month and
- The end day of the corresponding Treatment Period

#### 5.1.2 AE date imputation

Impute AE end date:

1. If the AE end date ‘month’ is missing, the imputed end date should be set to the earliest of the (min (last visit date, last dose date + 84 days), 31DECYYYY, date of death).
2. If the AE end date ‘day’ is missing, the imputed end date should be set to the earliest of the (min (last visit date, last dose date + 84 days), last day of the month, date of death).
3. If AE ‘year’ is missing or AE is ongoing, the end date will not be imputed.

Impute AE start date:

Before imputing AE start date, find the AE start reference date.

1. If the (imputed) AE end date is complete and the (imputed) AE end date  $<$  treatment start date then AE start reference date = min(informed consent date, earliest visit date).
2. Else AE start reference date = treatment start date
1. If the AE start date ‘year’ value is missing, the date uncertainty is too high to impute a rational date. Therefore, if the AE year value is missing, the imputed AE start date is set to NULL.
2. If the AE start date ‘year’ value is less than the treatment start date year value, the AE started before treatment. Therefore:  
If AE ‘month’ is missing, the imputed AE start date is set to the mid-year point (01JULYYYY).  
Else if AE ‘month’ is not missing, the imputed AE start date is set to the mid-month point (15MONYYYY).
3. If the AE start date year value is greater than the treatment start date year value, the AE started after treatment. Therefore:

- a. If the AE month is missing, the imputed AE start date is set to the year start point (01JANYYYYY).
  - b. Else if the AE month is not missing, the imputed AE start date is set to the later of (month start point (01MONYYYY), AE start reference date + 1 day).
4. If the AE start date year value is equal to the treatment start date year value:
  - a. And the AE month is missing the imputed AE start date is set to the AE reference start date + 1 day.
  - b. Else if the AE month is less than the treatment start month, the imputed AE start date is set to the mid-month point (15MONYYYY).
  - c. Else if the AE month is equal to the treatment start date month or greater than the treatment start date month, the imputed AE start date is set to the later of (month start point (01MONYYYY), AE start reference date + 1 day).

If complete (imputed) AE end date is available and the imputed AE start date is greater than the (imputed) AE end date, then imputed AE start date should be set to the (imputed) AE end date.

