12.5.2 Safety endpoints

All safety evaluations will be performed on the Safety set.

Adverse events

Treatment emergent AEs (events started after the first dose of study treatment and within 84 days after last dose, or events present prior to the first dose of study treatment but increased in severity based on preferred term within 84 days after last dose) will be summarized. Only primary paths within MedDRA will be considered for AE reporting.

AEs will be summarized by presenting, for each treatment group, the number and percentage of subjects having any AE, having an AE in each primary system organ class and having each individual AE (preferred term). Summaries will also be presented for AEs by severity and for study treatment related AEs. If a subject reported more than one AE with the same preferred term, the AE with the greatest severity will be presented. If a subject reported more than one AE within the same primary system organ class, the subject will be counted only once with the greatest severity at the system organ class level, where applicable.

Confidence intervals for relative frequencies will be derived as well according to the score method including continuity correction by Newcombe ([Newcombe 1998](#)).

Separate summaries will be provided for death, SAE, other significant AEs leading to discontinuation and AEs leading to study treatment discontinuation.

A graphical display of relative frequencies within system organ classes will be presented.

Vital signs

Analysis of the vital sign measurements using summary statistics for the change from baseline for each post-baseline visit will be performed. These descriptive summaries will be presented by vital sign and treatment group. Change from baseline will only be summarized for subjects with both baseline and post-baseline values.

Clinical laboratory evaluations

The summary of laboratory evaluations will be presented for two groups of laboratory tests (hematology and serum chemistry). Descriptive summary statistics for the change from baseline to each study visit will be presented. These descriptive summaries will be presented by test group, laboratory test and treatment group. Change from baseline will only be summarized for subjects with both baseline and post baseline.

For each parameter, the maximum change from baseline within each study treatment period will be analyzed analogously.

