Subjects who discontinue study treatment prematurely for any reason other than withdrawal of informed consent before Week 52 should not be considered discontinued from the study. Subjects should continue attending site visits for the study assessments. Subjects who are unwilling to continue the further study visits after discontinuing the study drug should attend the end of study visit. The End of Treatment visit (EOT 1 for discontinuation during Treatment Period 1 and EOT 2 for discontinuation during Treatment Period 2) should be performed two weeks (where possible) after their last dose of study drug. After the EOT visit, subjects should enter the post-treatment Follow-Up period.

Only subjects who prematurely discontinue the study in Treatment Periods 1 or 2 for any reason, or subjects who do not enroll in the extension study will enter the post-treatment Follow-Up and potentially complete the Week 60 visit.

[figure not shown]

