### **5.1.3 Concomitant medication date imputation**

Impute CM end date:

1. If CM end day is missing and CM month/year are non-missing then impute CM day as the minimum of treatment end date and the last day of the month.
2. If CM end day/month are missing and CM year is non-missing then impute CM day as the minimum of treatment end date and the end of the year (31DECYYYY).
3. If imputed CM end date is less than the CM start date, use the CM start date as the imputed CM end date.

Impute CM start date:

1. If the CM start date year value is missing, the imputed CM start date is set to one day prior to treatment start date.
2. If the CM start date year value is less than the treatment start date year value, the CM started before treatment. Therefore:
  - a. If the CM month is missing, the imputed CM start date is set to the mid-year point (01JULYYYY).
  - b. Else if the CM month is not missing, the imputed CM start date is set to the mid-month point (15MONYYYY).
3. If the CM start date year value is greater than the treatment start date year value, the CM started after treatment. Therefore:
  - a. If the CM month is missing, the imputed CM start date is set to the year start point (01JANYYYYY).
  - b. Else if the CM month is not missing, the imputed CM start date is set to the month start point (01MONYYYY).
4. If the CM start date year value is equal to the treatment start date year value:
  - a. And the CM month is missing or the CM month is equal to the treatment start date month, then the imputed CM start date is set to one day prior treatment start date.

- b. Else if the CM month is less than the treatment start date month, the imputed CM start date is set to the mid-month point (15MONYYYY).
- c. Else if the CM month is greater than the treatment start date month, the imputed CM start date is set to the month start point (01MONYYYY).

If complete (imputed) CM end date is available and the imputed CM start date is greater than the (imputed) CM end date, then imputed CM start date should be set to the (imputed) CM end date.

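### SAP 5.1.2 can move an adverse event with partial start and end dates from after the treatment-emergent window to inside it

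*SAP*

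**What the plan says.** **AE end dates (SAP 5.1.2).** With the day missing, the end is the "earliest of the (min (last visit date, last dose date + 84 days), last day of the month, date of death". With the month missing, it is the "earliest of the (min (last visit date, last dose date + 84 days), 31DECYYYY, date of death". If the year "is missing or AE is ongoing, the end date will not be imputed".

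**AE start dates (SAP 5.1.2).** A start with a known month, later than the month of first dose, becomes the later of the first of that month and the reference date plus one day. A start known only to fall in a year after the first-dose year becomes 1 January of that year. If an imputed start is later than the recorded or imputed end, "then imputed AE start date should be set to the (imputed) AE end date".

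**Window.** Protocol 12.5.2 counts "events started after the first dose of study treatment and within 84 days after last dose". SAP 2.6 includes the last day, last dose + 84.

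**Follow-up off drug.** Of patients who stop treatment early, SAP 1.1 says: "Subjects should continue attending site visits for the study assessments".

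**Medications (SAP 5.1.3).** With the day missing, the end-date rule is to "impute CM day as the minimum of treatment end date and the last day of the month". End-date rule 3 then moves an imputed end that precedes the start up to the start. A closing rule works the other way: if an imputed start is later than the end, "then imputed CM start date should be set to the (imputed) CM end date".

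**The concern.** The 84-day limit belongs to the definition of a treatment-emergent event, but 5.1.2 also uses it to impute an end date. Nothing keeps the result inside the recorded end month. The closing reset then carries the start back to the cap. An event whose record shows that it began after the window is thereby given a start on or before the last day of the window.

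Two AEs with the same recorded onset can be classified differently only because one has a partial stop date and the other is ongoing. That is an artefact of the rule, not a conservative convention.

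The plan makes the situation possible, because patients off drug are asked to keep attending and AEs are sought at each visit. A reset AE enters the crude treatment-emergent incidence and can add a patient to the numerator of the exposure-adjusted rate.

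**Working it through.** The plan states no figure to reproduce. The check applies the 5.1.2 rules literally to an illustrative patient.

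**Inputs (illustrative dates).** First dose 6 Jan 2020. Last dose at Week 12 (Day 85) = 30 Mar 2020. Window end = 30 Mar + 84 days = 22 Jun 2020. The patient stays on visits to Day 421 = 1 Mar 2021, and there is no death.

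**One AE, step by step: start Sep 2020, end Sep 2020, both days missing.**
1. End = earliest of min(1 Mar 2021, 22 Jun 2020) and 30 Sep 2020 = 22 Jun 2020.
2. Start = later of 1 Sep 2020 and 7 Jan 2020 (first dose + 1) = 1 Sep 2020.
3. 1 Sep is after 22 Jun, so the start is reset to 22 Jun 2020.
4. 22 Jun is the last day of the window, so the AE is flagged treatment-emergent.

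The earliest start that the record allows is 1 Sep, 71 days after the window closed.

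**All combinations with a recorded start after the window** (3 start patterns × 5 end patterns = 15):

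| Recorded start | Recorded end | Cases | Start moved into window |
|---|---|---|---|
| Partial (Sep 2020, or year 2021 only) | Partial, year known | 4 | 4 |
| Partial | Complete, year missing, or ongoing | 6 | 0 |
| Complete (10 Sep 2020) | Any | 5 | 0 |

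In 2 of the 5 complete-start cases the end is partial and is imputed as 22 Jun, before the recorded start. By the duration formula in SAP 2.1.1 (end − start + 1) this gives −80 + 1 = −79 days.

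A start known only as 2020 is treatment-emergent anyway, through the first dose + 1 rule, so the reset plays no part.

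**When the last visit is the cap.** For a completer with last dose at Week 50 (Day 351), last dose + 84 is Day 435, but the last visit is Day 365 or 421, so the last visit is the cap. With the same first dose, the window ends on 15 Mar 2021. An AE recorded Apr 2021 to Apr 2021 would be moved to 4 Jan or 1 Mar 2021. For a patient who stops both drug and visits, the end-of-treatment visit (about 14 days after last dose) plus 56 days puts the last visit at about last dose + 70, again below 84.

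**Expected number, on assumed inputs** (only 541 is from the documents). Formula: 541 × share stopping early × share of those followed past the window × follow-up in years × 3 AEs per patient-year × share with both days missing.
- Low: 541 × 0.10 × 0.25 × (20/52) × 3 × 0.01 = 0.16, about 0.2.
- High: 541 × 0.15 × 0.50 × (30/52) × 3 × 0.05 = 3.5.

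**Medications, same patient: a course recorded Jul 2020 to Sep 2020, days missing.** Take treatment end date as last dose (5.1.3 does not define it).
- End first, then closing reset: end = min(30 Mar, 30 Sep) = 30 Mar; start 1 Jul is reset to 30 Mar. The course counts as concomitant.
- Start first, then rule 3: start 1 Jul; end 30 Mar is moved up to 1 Jul. The course falls after 22 Jun and is not concomitant.

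The text does not say which order applies.

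**The case against.** **Reach.** A reader might infer that any AE with an unknown end date that began after the window becomes treatment-emergent. The text does not support that. Ongoing AEs and ends with a missing year are not imputed, and the reset is worded for an imputed start, so a complete recorded start stays put. Only 4 of the 15 patterns change. A reader might also infer that the cap is always last dose + 84 days; it is often the last visit. Both limits stand. In practice the exposed group is patients off drug who are still attending more than 84 days after their last dose. The completer cases need an AE dated after the last visit, which should be unusual: Protocol 10.1.3 sends SAEs beyond that visit to the safety database only.

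**Weight.** Crude tables count subjects by preferred term and the exposure-adjusted rate uses first occurrences, so a repeat of an earlier event changes nothing. An event placed at last dose + 84 falls at the censoring time, so exposure is unchanged. All AEs are listed with the flag, missing values are queried, and SAE documentation is fully source-verified. No event is hidden. All of this stands and keeps the point small. It does not make the date right.

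**Medications.** A reader might infer that 5.1.3 has the same fault, misdates therapies begun after stopping drug, and should lose its closing reset. The documents do not establish this. The outcome depends on an unstated order and an undefined term, and rule 3 already protects complete starts. The closing reset is also needed. With first dose on 6 Jan 2020, a missing start year is imputed as 5 Jan 2020. If the recorded end is complete and in 2019, only the closing reset stops the start from following the end.

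**Conclusion.** The point holds for a defined set of records. When AE start and end are both partial, the end year is known, and the recorded start month or year lies wholly after the window, 5.1.2 moves the start outside its recorded month or year to the cap, and the AE is wrongly flagged treatment-emergent. With a complete start after the window and a partial end, the flag is right but the imputed end precedes the start.

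The direction is certain: the error adds treatment-emergent events. The size is not known from the documents. The range of about 0.2 to 3.5 AEs rests on assumed discontinuation, follow-up, AE and missing-day rates. No efficacy analysis in this SAP is shown to depend on these dates. Section 5.1.3 needs a clarification of order, not a reversal. Severity: minor, but wrong as written and cheap to correct.

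**What to change.** **SAP 5.1.2**
- Remove last dose + 84 days from both end-date caps, or add the guard that 5.1.3 already has: an imputed end may not precede the start.
- State that no imputed date may leave its recorded month or year, and that the closing reset must not move a start out of its recorded month or year. This is needed with either option, because the last-visit cap can cause the same shift.
- Apply the 84-day limit only when setting the treatment-emergent flag.

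In the worked case the start then stays at 1 Sep 2020 and the AE is not treatment-emergent.

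**SAP 5.1.3**
- Keep both rules. State that when the medication end date was itself imputed, the end is moved to the start (rule 3), and that the closing reset of the start applies only when the recorded end is complete.

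**Cost.** A few sentences in the SAP and a small change to the date-imputation code. No new data are needed.

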### **5.1.3 Concomitant medication date imputation**

Impute CM end date:

1. If CM end day is missing and CM month/year are non-missing then impute CM day as the minimum of treatment end date and the last day of the month.
2. If CM end day/month are missing and CM year is non-missing then impute CM day as the minimum of treatment end date and the end of the year (31DECYYYY).
3. If imputed CM end date is less than the CM start date, use the CM start date as the imputed CM end date.

Impute CM start date:

1. If the CM start date year value is missing, the imputed CM start date is set to one day prior to treatment start date.
2. If the CM start date year value is less than the treatment start date year value, the CM started before treatment. Therefore:
  - a. If the CM month is missing, the imputed CM start date is set to the mid-year point (01JULYYYY).
  - b. Else if the CM month is not missing, the imputed CM start date is set to the mid-month point (15MONYYYY).
3. If the CM start date year value is greater than the treatment start date year value, the CM started after treatment. Therefore:
  - a. If the CM month is missing, the imputed CM start date is set to the year start point (01JANYYYYY).
  - b. Else if the CM month is not missing, the imputed CM start date is set to the month start point (01MONYYYY).
4. If the CM start date year value is equal to the treatment start date year value:
  - a. And the CM month is missing or the CM month is equal to the treatment start date month, then the imputed CM start date is set to one day prior treatment start date.

- b. Else if the CM month is less than the treatment start date month, the imputed CM start date is set to the mid-month point (15MONYYYY).
- c. Else if the CM month is greater than the treatment start date month, the imputed CM start date is set to the month start point (01MONYYYY).

If complete (imputed) CM end date is available and the imputed CM start date is greater than the (imputed) CM end date, then imputed CM start date should be set to the (imputed) CM end date.

